#### **1.4 Individual Subject Success and Overall Study Success Criteria**

Study success takes into consideration the purpose of the treatment and comparison to a control group as well as the study goals (e.g., superiority or equivalency). All primary evaluation parameters, at minimum, as well as safety information, should be accounted for in the definition of study success.

“Clinically meaningful improvement” (Intervention Responder) is defined for this proposed study as those subjects who 1) achieve no worse than one-eighth of the threshold of 0.44 m/s (1.0 mph) commonly used to represent gait speed associated with community ambulation, and 2) are free of a intervention-related complication in the active control group and the Ekso G intervention group.

Moreover, the Ekso G intervention and the active control group intervention will be considered an overall success if at least 85% of the per protocol population are defined as “Responders” and achieve the criteria specified for “Clinically Meaningful Improvement”.

Individual and overall success rates will be provided at each post-intervention evaluation interval (e.g., 6, 12, and 24 weeks).

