### **A. Primary Objective:**

To demonstrate that a 12 week robotic gait training regimen can lead to a clinically meaningful improvement in independent gait speed on the 10 Meter Walk Test (10MWT) in community dwelling

participants with chronic iSCI.

B. Secondary Objectives:

1. To examine the economic factors such as number of physical therapists/staff required during training.
2. To analyze the physical burden on therapists assisting and supervising during training.
3. To study the influence of factors that may modify the gait recovery in the chronic incomplete SCI population (demographic, clinical, functional, psychological, balance, etc.).

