### 1.3 Primary Endpoint

*Efficacy:* The primary endpoint is the mean increase in gait speed demonstrated during the 10MWT after 12 weeks/36 sessions of training compared to baseline and compared between groups. Both self-selected and fast speeds will be performed on the 10MWT, with the fast speed taking precedent.

Hypothesis #1: The mean change in the Ekso G intervention group will be statistically superior to that in the passive control group, as follows:

$$H_0: \mu_E \leq \mu_p \text{ vs } H_a: \mu_E > \mu_p$$

where  $\mu_E$  and  $\mu_p$  are the mean change in the Ekso G intervention group and the passive control group, respectively.

Hypothesis #2: Using the two one-sided (TOST) procedure, the null hypothesis of non-equivalence or non-inferiority of means will be tested for the Ekso GT ( $\mu_E$ ) versus the Active Control ( $\mu_A$ ) using a two-group design with equal sample sizes in the two groups. We want to demonstrate that the mean gait speeds will have similar distributions on the average for the two intervention groups. We specify that the practical difference in means is therefore defined to be 0.055 m/s, which is one-half of the hypothesized treatment effect of Ekso G over passive control as stated below, and one-eighth of the threshold of 0.44 m/s (1.0 mph) commonly used to represent gait speed associated with community ambulation. The two null hypotheses are specified below:

$$H_{01}: \mu_E - \mu_A \leq \delta_L \text{ or } H_{01}: \mu_E - \mu_A + \delta_U \leq 0 \text{ vs } H_{02}: \mu_E - \mu_A \geq \delta_L \text{ or } H_{02}: \mu_E - \mu_A - \delta_U \geq 0$$

The composite null hypothesis is that the two groups have unequal mean gait speeds. The alternative hypothesis is that the mean gait speeds are equivalent for both the Ekso G Intervention group and the active control group.

Reject  $H_{01}$  if the observed difference in the two means is too large. That is, reject if the lower bound for two-sided  $100(1-2\alpha)\%$  confidence interval for  $\mu_E - \mu_A$  is greater than the group mean multiplied by the assumed practical difference of 0.055 m/s.

Reject  $H_{02}$  if the observed difference in means is too small. That is, reject if the upper bound for the two-sided  $100(1-2\alpha)\%$  confidence interval for  $\mu_E - \mu_A$  is less than the group mean multiplied by the assumed practical difference of 0.055 m/s.

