#### **1.5 Overall Study Hypothesis**

The study hypothesis is directly related to the success criteria.

Accordingly, the null hypothesis of the study posits that there is no difference between the success probabilities for the Ekso G intervention and the active control intervention. Therefore, this trial of equivalence compares case success probabilities where the investigational intervention will be considered acceptable only if it can be demonstrated with 95% confidence ( $\alpha = 0.05$ ) that it is, at worst, 15% inferior to the active control intervention ( $\delta = 0.15$ ).

$$H_0: \pi_{\text{Ekso}} - \pi_{\text{Active Control}} \leq -0.15 \text{ vs. } H_a: \pi_{\text{Ekso}} - \pi_{\text{Active Control}} > -0.15$$

where  $\pi_i$  = the probability of subjects who achieve the success criteria that the difference in success probabilities is no more than 15% using the Blackwelder approach to testing equivalence of paired proportions.

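### SAP study success and the top-ranked hypothesis make no comparison with the passive arm, and that hypothesis is tested ahead of Ekso versus passive

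*SAP*

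**What the plan says.** The primary objective (Protocol section 2.A) is "To demonstrate that a 12 week robotic gait training regimen can lead to a clinically meaningful improvement in independent gait speed". SAP 1.3 and Protocol 17.2 give two efficacy hypotheses on change in 10MWT speed. The first reads "The mean change in the Ekso G intervention group will be statistically superior to that in the passive control group". The second compares Ekso with active control, with a margin of 0.055 m/s. The working hypothesis in SAP 1.2 also expects both trained groups to do better than the passive group.

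SAP 1.4 opens its success criteria by saying "All primary evaluation parameters, at minimum, as well as safety information, should be accounted for in the definition of study success". A responder must "achieve no worse than one-eighth of the threshold of 0.44 m/s", that is 0.055 m/s, and be free of an intervention-related complication. The Ekso and active-control interventions "will be considered an overall success if at least 85% of the per protocol population" are responders.

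SAP 1.5 states the null hypothesis of the study as being that "there is no difference between the success probabilities for the Ekso G intervention and the active control intervention", and tests it with a 15-point non-inferiority margin. SAP 1.6 orders the tests: the overall study hypothesis first, then the primary hypotheses, then the secondary ones, stopping at the first non-rejection.

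**The concern.** Participants in the passive arm are the only randomized comparators who receive no training. The Protocol predicts that Ekso will not be superior to matched manual training, so evidence that Ekso training improves gait speed has to come from Hypothesis #1. That hypothesis is in neither the success definition nor the overall study hypothesis, and it comes after the latter in the sequence.

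Two consequences follow. First, two equally ineffective trainings can look alike, so the top-ranked hypothesis can be won with no benefit over passive control, and a later failure of Hypothesis #1 does not undo that win. Second, if the top-ranked test fails, testing stops and Hypothesis #1, on which the primary objective depends, is never formally tested.

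**Working it through.** **Inputs (SAP 1.8).** Mean change and SD: Ekso 0.11 and 0.18, active 0.078 and 0.108, passive 0 and 0.108 m/s. Evaluable numbers are 38/38/19. The maximum of 127 at 2:2:1 gives 127 × 2/5 ≈ 51 per trained arm and about 25 passive. The SAP 1.5 margin is 0.15. Its alpha is 0.05 in SAP 1.5 but one-sided 0.025 in SAP 1.8, so both are shown.

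**The plan's own figures reproduce.**
- Hypothesis #1 at 38/19, two-sided 0.05: SE = √(0.18²/38 + 0.108²/19) = 0.0383; 0.11/0.0383 = 2.87; power = Φ(2.87 − 1.96) = 82% (80.5% with the Welch t). The smallest 2:1 sample reaching 80% is 38/19, as stated.
- Paired responder test: n = (1.960 + 0.842)² × 0.16/0.15² = 55.8, so 56, as stated.

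**Neither training works.** Give both trained arms the passive assumption (mean 0, SD 0.108), with normal changes and no complications. SAP 1.4 does not say whether 0.055 m/s is a required gain or a tolerated loss.
- Gain reading: responder share = 1 − Φ(0.055/0.108) = 30.5%.
- Tolerated-loss reading: Φ(0.055/0.108) = 69.5%.

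The variance p(1 − p) is the same for both readings, and so is the chance of winning. SAP 1.5 names a paired method, but the arms are independent groups, so an unpooled two-sample z test is used. At 38 per arm, SE = √(2 × 0.305 × 0.695/38) = 0.1057 and 0.15/0.1057 = 1.42. At 51 per arm, SE = 0.0912 and the ratio is 1.645.
- One-sided 0.05: Φ(1.42 − 1.645) = 41%; Φ(1.645 − 1.645) = 50%.
- One-sided 0.025: Φ(1.42 − 1.96) = 29%; Φ(1.645 − 1.96) = 38%.

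Exact binomial enumeration gives 41.4%, 50.2%, 29.5% and 38.2%. In the same case Hypothesis #1 is won in 2.5% of trials, so requiring it holds the chance at or below 2.5%.

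**Sensitivity at 38 per arm, one-sided 0.05 (exact).**
- Ekso mean 0 but SD 0.18, active like passive: the Ekso responder share is 38.0% (gain) or 62.0% (loss), and the test is won in 66% or 17% of trials.
- Active control as postulated: its share is Φ(0.023/0.108) = 58.4% on the gain reading. With Ekso like passive (30.5%) the test is won in 0.2% of trials; with Ekso SD 0.18 (38.0%), in 1.6%.
- 85% rule: it needs 33 of 38 responders. The chance is essentially 0 at 30.5% and 1.2% at 69.5%.

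**The reverse problem, at the planned effects.** On the gain reading the Ekso share is Φ(0.055/0.18) = 62.0%, against 58.4% for active. SE = 0.112; (0.036 + 0.15)/0.112 = 1.65. The normal approximation gives about 50% power and the exact figure is 49% (one-sided 0.05). Because Hypothesis #1 is tested only after this test is won, it can be formally won in at most about 49% of trials, against 80% on its own.

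**Adding Hypothesis #2 to the success definition.** At 38 per arm, SE = √((0.18² + 0.108²)/38) = 0.0341 and 1.645 × 0.0341 = 0.056, already wider than the 0.055 margin. A TOST result can then arise only when the observed SDs fall below plan. By simulation at the planned effects, Hypothesis #1 and the TOST are both won in about 1.5% of trials. With the one-sided non-inferiority test of Protocol 17.2 instead, the joint figure is about 72% at 38/38/19.

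**The case against.** A reader might infer that SAP 1.4 breaks its own rule. The text does not compel that. It speaks of evaluation parameters, not hypotheses, and SAP 1.6 counts one efficacy and one safety endpoint. A responder definition combining gait speed with freedom from complications can fairly be said to cover both. SAP 1.4's reference to study goals offers superiority or equivalency as alternatives and does not demand both. What stands is a design criticism: the definition leaves out the comparison on which the primary objective depends.

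A reader might also take 41% as the chance of declaring study success. It is not. Overall success in SAP 1.4 is the 85% rule, which would rarely be met at these rates on the gain or tolerated-loss reading. That protection is uncontrolled, however, and is not part of the SAP 1.5 test. It would be weak if 0.055 m/s meant an attained speed, which some participants may already reach at baseline.

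Nor is the exposure present whenever Ekso fails. If active control works as postulated and Ekso behaves like the passive arm, the top-ranked test almost never succeeds. The exposure is the case where both trainings fail, which is what a no-training arm is there to detect.

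Finally, Hypothesis #1 has not been dropped. It is primary, powered at 80%, and would be tested after a SAP 1.5 win, so its failure would be visible. A SAP 1.5 win on its own supports only a non-inferiority statement against active control. All of this is correct, but neither the ranking nor the success definition reflects it.

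**Conclusion.** The point holds in this form: success and the overall study hypothesis involve no comparison with passive control, and the overall hypothesis precedes Hypothesis #1 in the sequence. If neither training works, the SAP 1.5 test is won in about 41% of trials at 38 per arm and 50% at 51 per arm (one-sided 0.05), or 29% and 38% at one-sided 0.025. These figures assume mean change 0 and SD 0.108 in both trained arms, normal changes, independent arms, an unpaired test and no complications. They are sensitive to the Ekso SD and fall to about 0.2% if active control works as planned and Ekso behaves like the passive arm (gain reading). At the planned effects the ordering also limits the formal test of Hypothesis #1, because the test ahead of it has only about 49% power at 38 per arm (gain reading, one-sided 0.05). The matter should be corrected. It does not invalidate Hypothesis #1 or its sample size.

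**What to change.** In SAP 1.4 and 1.5, make rejection of Hypothesis #1 (Ekso superior to passive on 10MWT change) a required part of study success. In SAP 1.6, place Hypothesis #1 first in the fixed sequence, ahead of the Ekso-versus-active comparisons. Both changes are needed: the first alone leaves the SAP 1.5 test top-ranked and able to block Hypothesis #1.

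Do not also require Hypothesis #2 in its TOST form. If the Ekso-versus-active 10MWT comparison is to be part of success, use the one-sided non-inferiority test of Protocol 17.2 and state the joint power of about 72% at 38/38/19.

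The cost is a few lines of wording, with no new patients or data. Success can no longer be declared without the Ekso-versus-passive result, so its probability is capped at about 80% at 38/19. Any further required component lowers it; keeping the SAP 1.5 responder test as a joint requirement would hold it at or below about 49% (gain reading, one-sided 0.05).

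### SAP 1.4 leaves the 0.055 m/s responder cut-off undefined, yet the responder test ranks ahead of the gait-speed hypotheses and neither stated power (82%, 80%) describes it in this design

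*SAP*

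**What the plan says.** SAP 1.4 names the responder as someone with clinically meaningful improvement. It sets two conditions: to "achieve no worse than one-eighth of the threshold of 0.44 m/s (1.0 mph) commonly used to represent gait speed associated with community ambulation", and to have no complication related to the intervention. One-eighth of 0.44 is 0.055 m/s. SAP 1.3 uses the same figure as a margin between group means: "We specify that the practical difference in means is therefore defined to be 0.055 m/s".

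SAP 1.4 adds a success rule: each active intervention "will be considered an overall success if at least 85% of the per protocol population are defined as" responders. It reports the rates at several visits ("Individual and overall success rates will be provided at each post-intervention evaluation interval (e.g., 6, 12, and 24 weeks") and does not say which visit decides.

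SAP 1.5 builds the overall hypothesis on this responder: "The study hypothesis is directly related to the success criteria". In words, the null "posits that there is no difference between the success probabilities for the Ekso G intervention and the active control intervention". In symbols, it is a non-inferiority hypothesis with margin 0.15, at 95% confidence and alpha 0.05, tested "using the Blackwelder approach to testing equivalence of paired proportions".

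SAP 1.6 sets a fixed sequence at 0.05. It ranks the overall hypothesis above the primary endpoint hypotheses and ends testing once a hypothesis is not rejected.

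SAP 1.8 gives two powers for the responder analysis:
- 82% for a two-sided chi-square test of 85% (Ekso) against 55% (active control), with 38 per group.
- 80% for a paired equivalence test at one-sided 0.025, with 56 per group, no expected difference and 16% discordant pairs.

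**The concern.** The label speaks of improvement, which suggests a gain. The wording no worse than, and the reuse of a non-inferiority margin, suggest a tolerated loss. The bare figure could also be an absolute speed. No baseline reference, direction, walking speed or brace/device condition is given, so two analysts could build different responders from the same data.

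The rank of the test makes this serious. Protocol 17.2 has two gait-speed hypotheses and no gate before them, and the sample size in Protocol 17.4 and SAP 1.8 rests on those two. Under SAP 1.6, neither may be tested if the responder comparison fails. A reader of SAP 1.8 would take that gate to have about 80% power.

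**Working it through.** **Inputs (SAP 1.8).** Change in gait speed: Ekso mean 0.11, SD 0.18; active control 0.078, SD 0.108; passive control 0, SD 0.108 m/s. Planned sizes are 38/38/19. The maximum of 127 at 2:2:1 gives 127 × 2/5 = 50.8, about 51 per active arm. The gate margin is 0.15 (SAP 1.5).

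**1. The plan's own powers reproduce.**
- Chi-square, 0.85 against 0.55, n = 38: the pooled proportion is 0.70. Φ[(0.30 − 1.96 × √(2 × 0.70 × 0.30/38)) / √((0.85 × 0.15 + 0.55 × 0.45)/38)] = 82.8%.
- Paired, n = 56: Φ[0.15/√(0.16/56) − 1.96] = 80.1%.

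**2. The paired formula at the planned size.** With n = 38, 0.15/√(0.16/38) = 2.312. Power is Φ(2.312 − 1.960) = 64% at one-sided 0.025, or Φ(2.312 − 1.645) = 75% at 0.05. Ekso and active control are separate randomised arms, so there are no pairs to analyse.

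**3. Responder rates by reading** (normal changes, complications ignored).
- Gain of at least 0.055: Ekso Φ[(0.11 − 0.055)/0.18] = 62.0%; active control Φ[(0.078 − 0.055)/0.108] = 58.4%.
- Loss of at most 0.055: Ekso Φ[(0.11 + 0.055)/0.18] = 82.0%; active control Φ[(0.078 + 0.055)/0.108] = 89.1%. Some people who slowed would count as improved.
- Absolute speed of at least 0.055: not computable, because no baseline distribution is given.

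The expected difference therefore changes sign, from +3.6 to −7.1 percentage points.

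**4. The 85% rule.** With 38 in an arm, 0.85 × 38 = 32.3, so 33 responders are needed. Under the gain reading the binomial chance is below 0.1% in either arm. Under the loss reading it is 30% (Ekso) and 77% (active control).

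**5. Power of an unpaired gate.** Φ[(pE − pA + 0.15)/√((pE·qE + pA·qA)/n) − z], normal approximation, q = 1 − p:

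| Success rates | n = 38, one-sided 0.05 | n = 38, 0.025 | n = 51, 0.05 | n = 51, 0.025 |
|---|---|---|---|---|
| Gain, 62.0% / 58.4% | 50% | 38% | 61% | 48% |
| Loss, 82.0% / 89.1% | 26% | 17% | 31% | 21% |
| Both arms 85% | 57% | 45% | 68% | 56% |
| Both arms 95% (assumption) | 91% | 85% | 97% | 94% |

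Exact enumeration at n = 38 gives 49% and 40% for the gain row, and 60% and 45% for both arms at 85%. Under the gain reading, 80% power needs 86 per arm (0.05) or 109 (0.025).

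**6. Effect on the gait-speed tests.** Simulation with normal changes, Welch tests, the gain reading and the unpaired gate first:

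| Test | Sizes | No gate | Gate at 0.05 | Gate at 0.025 |
|---|---|---|---|---|
| Superiority over passive control, two-sided 0.05 | 38/38/19 | 80% | 45% | 36% |
| Non-inferiority to active control, one-sided 0.05 (Protocol 17.2) | 38/38/19 | 81% | 48% | 39% |
| Superiority | 51/51/25 | 90% | 58% | 46% |
| Non-inferiority | 51/51/25 | 90% | 60% | 48% |

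**7. Sensitivity to shape** (Pearson III, skewness −1 to +2, an assumption). Gain rates run from 68% to 50% (Ekso) and from 65% to 46% (active control), always below 85%. With the same skewness in both arms, gate power at 38 per arm stays at 50–52% (0.05) or 38–40% (0.025). With different skewness by arm it ranges over 5–96% or 3–92%. Loss-reading rates also move: at skewness +2 they are 92% and 100%.

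**The case against.** Several points on the other side stand.

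- **The weakness is not shown for every reading.** A reader might infer that the gate is underpowered however the cut-off is read. The documents do not support that. If an absolute-speed reading put both arms at 95%, power at 38 per arm would be 91% or 85%. For the same reason, it cannot be said that only the tolerated-loss reading comes near 85%.
- **The 80% is not for an unrelated test.** SAP 1.8 states it for this overall hypothesis, with the margin and the paired method of SAP 1.5. Its faults are the pairing, the 56 per arm and the alpha level. Only the 82% answers a different question.
- **An alternative with Ekso ahead is written down.** A reader might infer that no such alternative is stated anywhere. SAP 1.8 does set 85% against 55%. The trouble is that this conflicts with the non-inferiority hypotheses in SAP 1.5, with the zero difference assumed later in SAP 1.8, and with the prediction in the Protocol Study Outline that Ekso will not be superior to manual gait training.
- **The non-inferiority loss uses the protocol's test.** SAP 1.3 specifies two one-sided tests of equivalence for that comparison. With limits of ±0.055 at the planning values, their power is about 2% at 38 per arm and 10% at 51, so the gate would not be the main limit there. The superiority loss is unaffected.
- **Some details are partly settled elsewhere.** SAP 1.3 says of the primary endpoint: "Both self-selected and fast speeds will be performed on the 10MWT, with the fast speed taking precedent". Protocol 17.1 sets one-sided 0.05 for non-inferiority, which favours the 0.05 columns. The brace/device condition (Protocol Table 2, footnote 7) is open for the gait-speed endpoint as well.

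None of this supplies the missing direction and baseline reference, changes the order of testing, or creates pairs.

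**Conclusion.** The concern holds in this form and should be settled before analysis. Three parts rest on the text alone: the cut-off has no stated direction or reference, the comparison built on it comes first in the sequence, and a paired test is named for independent arms. The 80% power also assumes 56 per arm, when 38 are planned and about 51 are possible at most, and one-sided 0.025 where SAP 1.5 and 1.6 state 0.05.

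The size rests on the planning means and SDs, normal changes and no complications, which could only lower the success rates. Under the gain reading the 85% rule is practically out of reach, the unpaired gate has 50% or 38% power at 38 per arm, and the chance of showing superiority over passive control falls from about 80% to 45% or 36%. The loss reading gives a weaker gate still (26% or 17%). These are not firm forecasts: gate power depends strongly on any difference in skewness between arms, and it would be adequate at much higher success rates.

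**What to change.** 1. **SAP 1.4:** state the responder as a change from baseline of at least +X m/s at week 12, and name the speed and the brace/device condition. Justify X for individuals against the protocol's 0.15 m/s MCID (Protocol 4).
2. **SAP 1.6:** rank the responder comparison below the two gait-speed hypotheses.
3. **SAP 1.5:** replace the paired test with an unpaired non-inferiority test at one stated alpha, with its sidedness.
4. **SAP 1.8:** delete the 85% against 55% statement and the paired power statement, or restate both as the unpaired power of the SAP 1.5 test at the planned size.
5. **SAP 1.4, 85% rule:** reconcile it with the planning values or label it descriptive.

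The cost is SAP wording only; no new data are needed. The downside for the sponsor is a less favourable stated power for the responder test (about 38–50% at 38 per arm if X were 0.055) and the loss of that test's first rank.

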#### PHYSICAL PERFORMANCE OUTCOMES

10MWT for both self-selected and fast gait speed

Number of participants who achieve the Minimal Clinically Important Difference (MCID) of 0.15 m/s during the 10MWT

Number of participants who transition from exercise or household ambulation (defined as self-selected walking speed of < 0.44 meters/second) to limited community or full community ambulation ( $\geq 0.44$  meter/second) during the self-selected 10MWT

Time point of recovery at which participants reach the MCID and/or community ambulation speeds of  $\geq 0.44$  meters/second

6MWT for endurance

Timed Up and Go (TUG) for balance during sit-to-stand, walking, turning, and stand-to-sit

WISCI-II score for need of assistance and devices

SCI-FAI for observational gait quality

GAITRite for temporospatial gait parameters and symmetry (if site has access to this device)

SCIM-III, mobility subscale for ability to perform transfers and walking different distances

Berg Balance Scale for measurement of static balance and dynamic sitting and standing balance.

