### **17.2 Primary Endpoint**

The primary endpoint is change in gait speed (self-selected and fast) demonstrated during the 10MWT after 12 weeks of training, compared to baseline. Two hypotheses are associated with this endpoint; first, that the mean change in the Ekso intervention group will be statistically superior to that in the passive control group, as follows:

$$\begin{aligned} H_0: \mu_E &\leq \mu_P \\ H_A: \mu_E &> \mu_P, \end{aligned}$$

where  $\mu_E$  and  $\mu_P$  are the mean change in the Ekso and passive control groups, respectively. The hypothesis will be tested using a two-sample Student's t or Wilcoxon rank-sum depending upon normality of the trial data.

The second hypothesis is that the mean change in the Ekso intervention group will be statistically non-inferior to that in the active control group, as follows:

$$\begin{aligned} H_0: \mu_E &\leq \mu_A - \Delta \\ H_A: \mu_E &> \mu_A - \Delta, \end{aligned}$$

where  $\mu_E$  and  $\mu_A$  are the mean change in the Ekso and active control groups, respectively, and  $\Delta$  is the non-inferiority margin.  $\Delta$  is selected based upon the principles that it should be substantially less than the expected effect size comparing Ekso to passive control, and that it should represent a clinically acceptable margin of effect when differentiating Ekso from active control.

For this purpose,  $\Delta$  is therefore defined to be 0.055 m/s, which is one-half of the hypothesized treatment effect of Ekso over passive control as stated below, and one-eighth of the threshold of 0.44 m/s (1.0 mph) commonly used to represent gait speed associated with community ambulation.

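### The SAP's responder cutoff for clinically meaningful improvement, 0.055 m/s, is 37% of the protocol's own 0.15 m/s MCID, yet it drives the success rule and the top-ranked hypothesis

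*SAP*

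**What the plan says.** SAP 1.4 defines clinically meaningful improvement (the intervention responder) by two conditions. The subject must "achieve no worse than one-eighth of the threshold of 0.44 m/s (1.0 mph) commonly used to represent gait speed associated with community ambulation", and must also be among those who "are free of a intervention-related complication in the active control group and the Ekso G intervention group". The section prints neither the value 0.055 nor the word gain.

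The responder then carries weight in three places:
- **SAP 1.4:** overall success requires at least 85% responders in the per-protocol population, with rates reported at 6, 12 and 24 weeks.
- **SAP 1.5:** the overall study hypothesis compares responder probabilities between Ekso and active control with a 15-point margin.
- **SAP 1.6:** that hypothesis is placed ahead of the primary endpoint hypotheses in a fixed sequence that stops at the first non-rejection.

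The protocol's Study Outline and section 4 both list as a secondary endpoint the "Number of participants who achieve the Minimal Clinically Important Difference (MCID) of 0.15 m/s" on the 10MWT. The SAP does not mention this MCID. Its only 0.15 is the margin on proportions.

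The value 0.055 m/s appears elsewhere in another role. SAP 1.3 states: "We specify that the practical difference in means is therefore defined to be 0.055 m/s". Protocol 17.2 uses the same value as the non-inferiority margin, on the principle that "it should represent a clinically acceptable margin of effect when differentiating Ekso from active control".

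**The concern.** The protocol's primary objective is a clinically meaningful improvement in gait speed, and SAP 1.4 is where the plan gives that phrase an operational definition. The cutoff chosen is well below the MCID that the protocol adopts for the same test, and no reason for the departure is given. Read as a gain, a change of 0.06 m/s makes a subject a clinically meaningful responder under the SAP and a miss on the protocol's MCID count, in the same report.

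Because the responder hypothesis stands first in the testing sequence, the definition also decides whether the primary gait-speed hypotheses are formally tested at all. The one-eighth-of-0.44 derivation is the one given for the non-inferiority margin. That suggests the number was carried over rather than chosen as an individual benefit threshold.

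**Working it through.** **Inputs.** Planning changes (Protocol 17.4, SAP 1.8): Ekso mean 0.11, SD 0.18; active control 0.078, SD 0.108; passive control 0, SD 0.108 (all m/s). MCID 0.15 m/s (Protocol 4). Planned evaluable 38 per active arm.

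**The plan's own figures.** 0.44/8 = 0.055 and 0.11/2 = 0.055, so both stated derivations agree. Non-inferiority of means at one-sided 0.05 and 80% power: (0.18² + 0.108²) × ((1.645 + 0.842)/(0.055 + 0.032))² = 36.0 per group. A Welch t calculation gives 79.2% power at 36 and 80.2% at 37, so the stated 37 reproduces.

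**Cutoff against MCID.** 0.055/0.15 = 0.367, or 37%.

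**Responder rates.** P(change ≥ c) = 1 − Φ((c − mean)/SD), assuming normal changes, the cutoff read as a gain, and the complication condition ignored (it can only lower the rates).

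| Arm | c = 0.055 | c = 0.15 |
|---|---|---|
| Ekso | 1 − Φ(−0.306) = 62.0% | 1 − Φ(0.222) = 41.2% |
| Active | 1 − Φ(−0.213) = 58.4% | 1 − Φ(0.667) = 25.2% |
| Passive | 1 − Φ(0.509) = 30.5% | 1 − Φ(1.389) = 8.2% |

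**Responders at 0.055 m/s who miss the MCID.** Ekso: 1 − 41.2/62.0 = 34%. Active: 1 − 25.2/58.4 = 57%.

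**Other readings.** As a tolerated loss (change ≥ −0.055) the rates are Ekso 82%, active 89%, passive 69%, which is weaker still. Neither change-score reading reaches 0.15 m/s. As an absolute speed, the rate cannot be computed because the documents give no baseline distribution.

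**The 85% bar.** 0.85 × 38 = 32.3, so 33 responders are needed in an arm of 38. The binomial probability of at least 33 of 38 at 0.055 m/s is 0.0007 for Ekso and 0.0002 for active control. At 0.15 m/s it is below 10⁻⁷ for both.

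**Effect on the SAP 1.5 comparison.** Expected Ekso minus active: 62.0 − 58.4 = 3.6 points at 0.055 m/s; 41.2 − 25.2 = 16.0 points at 0.15 m/s. Treating the arms as independent proportions with 38 each, a 15-point margin and one-sided 0.05, power = Φ((0.15 + difference)/SE − 1.645):
- at 0.055 m/s, SE = 0.112, power about 50%;
- at 0.15 m/s, SE = 0.107, power about 90%.

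The widening comes from the assumed SDs. If Ekso's SD were 0.108 like the other arms, its rates would be 1 − Φ(−0.509) = 69.5% and 1 − Φ(0.370) = 35.6%, and the differences 11.0 and 10.3 points, with no widening.

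**The case against.** Several stronger readings are tempting, and the documents do not support them.

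- **A reader might infer that one number cannot be both negligible and meaningful.** A margin on a difference between group means and a threshold for one person's change are different quantities and may share a value. Neither document calls 0.055 m/s negligible. The reuse is supporting evidence only.
- **A reader might infer that the low cutoff makes overall success easy.** On the planning figures the 85% bar is almost out of reach even at 0.055 m/s. Only the comparative hypothesis in SAP 1.5 could realistically be positive.
- **A reader might stress that 3 in 10 untrained controls would meet the speed cutoff.** That follows from the assumptions, but the passive arm enters neither the 85% rule nor the SAP 1.5 comparison.
- **A reader might assume the 85% and 15-point figures were derived from 0.055 m/s.** Neither document says so.

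The strongest defence is that the primary endpoint is mean change, which this cutoff does not touch, and that the MCID count is already planned, so the report would simply carry two counts. It adds that SAP 1.4 never states a gain, so the first defect is an undefined criterion. Both facts are correct. They do not remove the conflict: the lower count carries the clinically meaningful label and stands first in the testing order, and neither change-score reading brings the criterion up to the MCID.

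**Conclusion.** The point holds as an inconsistency with the trial's own standard. The SAP's decision threshold for clinically meaningful improvement is 0.055 m/s against a protocol MCID of 0.15 m/s, is not defined as a gain, a loss or a speed, and has no stated justification as an individual threshold. Success on it would not support the primary objective as the protocol measures clinical importance.

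The shortfall of 34% of Ekso and 57% of active-control responders rests on the planning means and SDs, normality, the gain reading and no complications. Whether 0.15 m/s is itself the right MCID cannot be checked from these documents. It should be settled before the analysis because the top-ranked hypothesis depends on it.

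**What to change.** In SAP 1.4:
1. Define the gait criterion as a gain from baseline of at least 0.15 m/s on the 10MWT.
2. State whether it applies to fast or self-selected speed. The protocol's MCID endpoint does not say, while the primary endpoint gives precedence to fast speed.
3. Apply it at each reported visit, with week 12 as the decision visit.
4. Keep 0.055 m/s only as the between-arm margin. If the sponsor prefers a lower responder cutoff, it should be justified and must not be called clinically meaningful.

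Recheck the 85% bar and the responder power statements in SAP 1.8 (0.85 against 0.55 with 38 per group, and the equivalence statement with 56 per group).

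No new data are needed, since the 10MWT is already collected and the MCID count already planned. The cost is a SAP edit plus the recalculation. The consequences run both ways and should be disclosed: expected responder rates fall (Ekso 62% to 41%, active control 58% to 25%), while the SAP 1.5 non-inferiority comparison becomes easier for Ekso to pass because of its larger assumed SD. The change should therefore be made and dated before unblinded outcome data are seen.
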